3.3.2. Secondary Endpoints

Visit 1a or Visit 1b will serve as the baseline visit for efficacy endpoints. Visit 1a will be the Baseline for patients directly entering the Treatment Period as of Visit 1a. Visit 1b will be the Baseline for patients entering the Treatment Period after participating in the Observation Period for any length of time.

The secondary endpoints are:

- Assess skin lesion improvement using the metrics of the PAS
- Change from Baseline in PRO measures Worst itch NRS, average itch intensity NRS, VRS (itchy, burning and stinging), MOS-Sleep-R, ItchyQoL, HADS by Treatment Period study visit and Baseline NRS score
- Change between Baseline and the final Treatment Period visit in PBI-P
- A description of the percentage of patients utilizing various doses of nalbuphine HCl ER tablets by study week
- A description of the frequency and reasons for dose up-and down-titration and treatment discontinuation during the study
- Frequency and distribution by time on study of patients determined to meet failure-to-improve criterion
- Changes in the PRO measurements during the Washout Period after cessation of treatment of nalbuphine HCl ER tablets
- Time to first use of rescue medications and the number of days of use of rescue medications for itching
- To evaluate the daily changes in the SOWS during the Washout Period after cessation of treatment of nalbuphine HCl ER tablets.

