4.1. General Methodology

Continuous data will be described using descriptive statistics including patient count (n), mean, standard deviation (SD), median, minimum, and maximum. Categorical data will be described using the patient count and percentage in each category. The percentage will be suppressed when the count is zero for a category in order to draw attention to the non-zero counts. Where specified on the table shells, a row denoted "Missing" is to be included in count tabulations to account for dropouts and missing values. The denominator for all percentages will be the number of patients in that treatment arm within the analysis population of interest, unless otherwise specified.

Patients will be identified in the listings by the patient identification number concatenated with the investigator/site number. Data will be displayed in all listings sorted by patient identification number concatenated with the investigator/site number. Data listings, unless otherwise specified, will include all patients who provide consent to participate in the study.

Unscheduled results will not be included in the summary tables except for determining Baseline values for efficacy and safety evaluations and the handling of laboratory data both at Baseline and during treatment (see Section 4.2). For patients discontinuing from the study, planned study visit data that are collected at the early termination visit will be included in by-visit summaries in the summary tables or figures (e.g. PRO questionnaires) using the serial next visit number associated with what would have been the patient's next scheduled visit. Thus, for example, a patient discontinuing from the study after Treatment Visit 2 would have efficacy and safety data obtained at the study termination visit treated as Treatment Visit 3 results. Data listings will include all data from scheduled, repeated, unscheduled and early termination visits.

All p-values will be rounded to three decimal places. If a p-value is less than 0.001 it will be reported as "<0.001." If a p-value is greater than 0.999 it will be reported as ">0.999." Point estimates of the parameter of interest will be generated along with, where appropriate, 95% confidence intervals.

All analyses will be conducted using SAS Version 9.2 or higher.

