9.2. Other Safety Assessments

9.2.1. SOWS

The SOWS is a self-administered scale for grading opioid withdrawal symptoms. It contains 16 symptoms whose intensity the patient classifies as: 0=“not at all”, 1=“a little”, 2=“moderately”, 3=“quite a bit”, and 4=“extremely”. In this study, patients will complete the SOWS daily, starting at the TV14, End of Treatment visit through to the Washout and Safety Follow-up Period visit. The SOWS will also be completed at the Premature Discontinue of Study Drug Treatment visit. As with all patients who are discontinued from study drug, the patient will complete a daily SOWS scale for the two weeks following the last dose of study drug (unless consent is withdrawn).

To evaluate the daily changes in the SOWS during the Washout Period after cessation of treatment, each of the 16 symptom items will be summarized for each of the first 14 days beginning with the End of Treatment visit as frequencies and percentages of patients. No formal analysis will be undertaken. Additionally, the sum of all non-missing responses for the 16 items (SOWS total score) will be derived and similarly presented for each of those 14 days.

The change from the End of Treatment visit (defined as the maximum SOWS total score across days from the End of Treatment visit date to 7 days following the End of Treatment visit date), to the Washout and Safety Follow-up visit (defined as the SOWS total score on the date of the Washout and Safety Follow-up Period or the latest date following the End of Treatment Visit and before the Washout and Safety Follow-up visit) will be summarized using descriptive statistics for each treatment group.

A categorical summary will also be provided for the number and percentage of patients by their highest observed SOWS total score during the 14-day (washout) period already defined. The categories will be: ≤ 10 , 11-20, 21-30, 31-40, 41-50, 51-60, >60 . No formal analysis will be undertaken.

Maximum SOWS symptom score (defined for each patient for each day of the Washout and Safety Follow-up Period as the maximum (i.e. worst) non-missing score across all 16 symptom items) will be summarized using descriptive statistics for each treatment group.

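### The SOWS endpoint is daily change during washout, but section 9.2.1 gives only daily levels, and its one change score starts from a maximum that includes the week after End of Treatment

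*SAP*

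**What the plan says.** Section 3.3.2 lists as a secondary endpoint "To evaluate the daily changes in the SOWS during the Washout Period after cessation of treatment of nalbuphine HCl ER tablets". Section 2.2 has the same item among the secondary objectives.

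Section 9.2.1 restates that purpose and gives these outputs:

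- **Items, by day:** "each of the 16 symptom items will be summarized for each of the first 14 days beginning with the End of Treatment visit as frequencies", given with the matching percentages.
- **Total, by day:** "the sum of all non-missing responses for the 16 items (SOWS total score) will be derived and similarly presented for each of those 14 days".
- **Worst item score, by day:** each patient's highest item score on each washout day, with descriptive statistics.
- **Peak:** patients classified by their highest total over the 14 days, in seven categories.
- **One change score:** from End of Treatment to the Washout and Safety Follow-up visit. The End of Treatment value is "defined as the maximum SOWS total score across days from the End of Treatment visit date to 7 days following the End of Treatment visit", counted by calendar date. The end value is the total on the Washout visit date, or the latest one before it.

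The scale has 16 items scored 0 to 4. Patients complete it daily from the End of Treatment visit (TV14), so a first-day value is collected. Section 4.1 adds a general rule: "Continuous data will be described using descriptive statistics including patient count (n), mean, standard deviation (SD), median, minimum, and maximum".

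**The concern.** The endpoint is worded as change, but every by-day output is a level. A level table shows how patients score on a given day. It does not show how many of them are worse than when they stopped, or on which day they became worse. Elsewhere the SAP specifies change where it wants it: section 8.1 for the PROs from baseline, section 8.2 for the PROs from End of Treatment to Washout, and section 9.3 for laboratory values at every post-baseline visit.

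The single SOWS change score might seem to make up for this, but its start value can be a score recorded after treatment has stopped. A patient whose symptoms rise in the first week and then settle is recorded as having improved. The study's primary objective is safety and tolerability, so a reader of the report could take a negative mean change as evidence against withdrawal.

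**Working it through.** The plan gives no figure to reproduce here: there is no sample size calculation and nothing is tested. The check has three parts.

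**1. Does any output give within-patient change by day?**

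| Output in section 9.2.1 | By day? | Within-patient change? |
|---|---|---|
| Item frequencies | yes | no |
| Total score | yes | no |
| Worst item score | yes | no, a 0-4 level |
| Highest total over 14 days | no | no |
| Change to the Washout visit | no | yes, but from a maximum |

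No row has yes in both columns.

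**2. What does the change score measure?** Let T0 be the total on the End of Treatment date, T1 to T7 the totals on the next seven days, and Tw the total at the Washout visit. The SAP's change is Tw - M, where M = max(T0, ..., T7), a maximum over 8 calendar days. When T0 is recorded, M is at least T0, and

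Tw - M = (Tw - T0) - (M - T0).

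The subtracted term, M - T0, is the patient's largest rise over the End of Treatment day during the first week. The score therefore goes down by exactly the amount of early worsening.

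An illustrative course, all values assumed, expressed relative to the End of Treatment day: 0, 4, 8, 10, 8, 6, 4, 3 on days 0 to 7, back to 0 by the Washout visit. Without noise, the SAP's change is 0 - 10 = -10. Change from day 0 is 10 - 0 = +10 on day 3 and 0 at the end.

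With normal day-to-day noise added (within-patient SD of 1, 2 or 4 points, assumed because the SAP gives none; complete data; simulated means):

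| Assumed SD | Flat course, SAP change | Peak of 10 on day 3, SAP change | Same peak, day-3 change from day 0 |
|---|---|---|---|
| 1 | -1.4 | -10.1 | +10.0 |
| 2 | -2.9 | -10.7 | +10.0 |
| 4 | -5.7 | -12.7 | +10.0 |

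The flat-course column can be checked directly. The expected maximum of 8 independent standard normal values is 1.424, so the expected change is -1.424 x SD, or -1.42, -2.85 and -5.69. The score is negative even when nothing happens.

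In the same simulation the daily means reproduce the assumed rise and fall (0, 4, 8, 10, 8, 6, 4, 3). With complete diaries, the group-level course is visible by day.

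**3. What if diaries are lost selectively?** This is an assumption; the SAP reports no such loss. Let each patient's total be constant for 14 days (gamma-distributed, mean 8.4, shape 1 to 1.5), with a daily probability of stopping the diary whose logit is -4.2 + 0.08 x score. About 67% still report on day 14. Among those reporting, the mean falls from 8.4 to between 6.2 and 6.8, and the share above 20 falls from 7-9% to about 3%, although no patient has changed. Change from day 0 among patients with both values is 0 on every day.

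**The case against.** The strongest reply is that describing the course day by day is a fair reading of the endpoint. The text says to evaluate daily changes, not change from a reference value. Section 9.2.1 opens with that same purpose and then gives its method, in a study with no inferential analysis. Fourteen consecutive daily distributions starting at End of Treatment do show when symptoms emerge in the group. The peak table gives each patient's worst total, and section 9.1.7 summarises abuse- and withdrawal-related events for the washout period. All of this stands, and it limits the point to the within-patient view.

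Three stronger readings are tempting, and the SAP does not support them.

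- *That the daily outputs are only frequencies.* The worst item score is summarised by day with descriptive statistics.
- *That the total will be printed as a raw frequency table.* Sixteen items scored up to 4 give a maximum of 16 x 4 = 64, so 65 values and 65 x 14 = 910 cells over 14 days. That rests on a literal reading of how the total is to be presented. Section 4.1 prescribes mean, SD and so on for continuous data, the table shells are not shown, and unobserved values need not be printed. The wording is ambiguous; a table without mean or spread is not established.
- *That diary loss will distort the tables.* Section 9.2.1 expects daily completion unless consent is withdrawn. Section 4.7 rules out imputation, so loss would matter if it occurred, but its size and direction are unknown. A row for missing values, which section 4.1 allows where the shells specify it, would make the loss visible.

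There is also a fair caution about the remedy. TV14 follows the last week of study drug (section 3.1), and patients who stop early attend it after stopping (sections 3.2.1 and 3.2.2), so the TV14-date score is not always a clean pre-withdrawal value. The total is also a sum of answered items, so one skipped item can lower it by up to 4 points and look like change. Both need handling, but neither supports using a maximum over the following week.

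**Conclusion.** The point holds in a limited form. The SAP names daily change in SOWS as a secondary endpoint, and no planned output shows a patient's change by day, how many patients worsened from their own End of Treatment score, or on which day. A reader might infer that emerging withdrawal would go unseen; that goes too far, because the daily summaries show it at group level when diaries are complete.

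The planned change score cannot stand in for the missing output. It is biased downward by construction: its shortfall against change from the End of Treatment day equals the largest first-week rise. The direction follows from the definition. The sizes in the working (-1.4 to -5.7 for a flat course, -10.1 to -12.7 for a transient 10-point rise) depend on the assumed noise and course. The diary-loss figures rest wholly on assumptions and are secondary.

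This is a worthwhile and inexpensive improvement to a named secondary safety endpoint. It does not invalidate the other SOWS outputs.

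**What to change.** Amend section 9.2.1 as follows.

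1. For each washout day, summarise the SOWS total with n, mean, SD, median, minimum and maximum. This also settles the ambiguity in how the daily total is presented.
2. For each day after TV14, summarise in the same way the within-patient change from the total recorded on the TV14 date, among patients with both values. Report the number and percentage of those patients whose total rose from that reference. A rise of any size includes day-to-day noise, so read the count beside the change statistics.
3. Use the TV14-date total as the start value of the change to the Washout visit, in place of the maximum over days 0 to 7. The peak table can stay as the summary of the worst score.
4. Flag, or present separately, patients whose TV14 took place some days after their last dose.
5. Compute change only where the same items were answered on both days.

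The cost is SAP wording and programming for a few extra descriptive tables. The daily scores are already collected, so no new data are needed.

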2.2. Secondary Objectives

The secondary objectives of the study are:

- To evaluate the safety of nalbuphine by achieved maintenance dose at the end of Treatment Week 4,
- To assess skin lesion improvement using the metrics of the Prurigo Activity Score (PAS),
- Change from Baseline in Patient-Reported Outcome (PRO) measures Worst (i.e. most severe itching over the past 24 hours) itch Numerical Rating Scale (NRS), average itch intensity NRS, Verbal Rating Scale (VRS) (itchy, burning and stinging), Medical Outcomes Scale (MOS) Sleep-R, ItchyQol, and Hospital Anxiety and Depression Score (HADS) by the final Treatment Period Visit,
- Change between Baseline and the final Treatment Period Visit in Patient Benefit Index, pruritus version (PBI-P),
- A description of the percentage of patients utilizing various doses of nalbuphine HCl ER tablets by Study Week,
- A description of the frequency and reasons for dose up-and down-titration and treatment discontinuation during the study,

- Frequency and distribution by time on study of patients determined to meet failure-to-improve criteria,
- Changes in the PRO measurements during the Washout Period after cessation of treatment of nalbuphine HCl ER tablets,
- Time to first use of rescue medications and the number of days of use of rescue medications for itching,
- To evaluate the daily changes in the Subjective Opiate Withdrawal Scale (SOWS) during the Washout Period after cessation of treatment of nalbuphine HCl ER tablets.

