The total amount of time in the Observation Period cannot exceed 12 weeks. After these 12 extended screening weeks, patients not eligible for the Treatment Period are screen failed from the study. The study periods are summarized below.

Study Period	Study Weeks	Duration
Observation Period	
Patients who do not meet the criteria to start Treatment are followed in Observation Period visits (OV) for up to 12 extended screening weeks. During this time, the patient may meet criteria and become eligible to enter the Treatment Period. If the patient does not meet the criteria to enter the Treatment Period by the end of 12 extended screening weeks (OV12), participation in the study ends and the patient is screen failed
	Up to 12 Extended Screening weeks
Treatment Period	
For patients directly entering the Treatment Period as of Visit 1a, the Treatment Period begins with Study Week 1 (Visit 1a) and ends with Study Week 50.
 
For patients entering the Treatment Period after being followed in the Observation Period, the number of weeks on treatment and the end of the Treatment Period varies. (See Table 8 in the study protocol for the details of which treatment visits are to take place).
 
The End of Treatment Visit will take place after the patient completes the last week of study drug.
	Up to 50 weeks
Washout and Safety Follow-Up Period	
The Washout and Safety Follow-up Period is two (2) weeks in duration.
 
For patients directly entering the Treatment Period as of Visit 1a and completing 50 weeks of study drug treatment, the Washout and Safety Follow-up Period should take place during weeks 51 and 52.
 
For patients entering the Treatment Period after being followed in the Observation Period, the number of weeks on treatment and the end of the Treatment Period varies; Table 8 in the Study Protocol calculates the Treatment Visit assignments for any patient entering the Treatment Period from the respective Observation Period visits. The Washout and Safety Follow-up Period will take place during the two (2) weeks after the patient completes the last week of study drug.
 
The Washout and Safety Follow-up Period Visit will take place in the week following the completion of the two (2) week Washout and Safety Follow-up Period.
	2 weeks

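### The SOWS change from the End of Treatment visit starts from the worst score of the first 8 days, so this one summary is biased towards improvement

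*SAP*

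**What the plan says.** One secondary objective (SAP Section 2.2) is: "To evaluate the daily changes in the Subjective Opiate Withdrawal Scale (SOWS) during the Washout Period after cessation of treatment". Section 9.2.1 states the collection schedule: "patients will complete the SOWS daily, starting at the TV14, End of Treatment visit through to the Washout and Safety Follow-up Period visit". For patients taken off drug, "the patient will complete a daily SOWS scale for the two weeks following the last dose of study drug".

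The same section then defines a change score. Its starting value, named for the End of Treatment visit, is "defined as the maximum SOWS total score across days from the End of Treatment visit date to 7 days following" that visit. Its end value is a single day's total, "defined as the SOWS total score on the date of the Washout and Safety Follow-up Period or the latest date following the End of Treatment" (with the follow-up visit as the limit). The total itself is a plain sum: "the sum of all non-missing responses for the 16 items (SOWS total score) will be derived".

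The study-period table in Section 3.1 fixes the timing: "The End of Treatment Visit will take place after the patient completes the last week of study drug", and "The Washout and Safety Follow-up Period is two (2) weeks in duration".

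Section 9.2.1 also plans four other displays: each of the 16 items by day for 14 days, the total for each of those days, patients grouped by their highest total over the 14 days, and the daily maximum symptom score.

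**The concern.** The label and the definition do not match. The label promises a change measured from the end of treatment. The definition takes the worst score from the visit date and the week after it, which is washout time. Withdrawal that appears in that week goes into the reference value and is then subtracted.

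Section 8.2 treats the other patient-reported outcomes differently: their washout change runs from the End of Treatment visit itself to the follow-up visit. Only the withdrawal scale uses a post-visit maximum under the same visit name.

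What is at stake is how a safety table is read. A reader who sees a negative mean change from End of Treatment will conclude that symptoms eased after the drug was stopped, when the sign may come from the definition alone.

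**Working it through.** The SAP gives no SOWS figure to reproduce (no SD, mean or correlation), so the check is of the definition.

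**Inputs from Section 9.2.1.** Reference: maximum over day 0 to day 7, that is 7 - 0 + 1 = 8 daily scores. End value: one daily score, nominally about day 14. Scale: 16 items scored 0 to 4, so 0 to 64. Share of washout: 8 days out of two weeks, slightly more than half.

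**Direction, without assumptions.** Let Y0 to Y7 be the daily totals in the window and YL the last one. When Y0 is observed, max(Y0, ..., Y7) is at least Y0, so YL - max(Y0, ..., Y7) can never exceed YL - Y0. The planned change is therefore at or below the change from the visit day in every such patient. If the last diary entry falls on or before day 7, YL is itself inside the maximum and the change cannot exceed 0.

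**Size, under assumptions.** For 8 independent normal scores the expected maximum is 1.42 SD above the mean, so the expected change with no true change is -1.42 within-patient SD. A simulated first-order autoregressive normal series over days 0 to 14 gives, in within-patient SD:

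| Day-to-day correlation | Flat series, SAP change | Sustained +5 SD from day 3, SAP change | +5 SD starting after day 7, SAP change |
|---|---|---|---|
| 0 | -1.42 | -1.16 | +3.6 |
| 0.5 | about -1.24 | -0.95 | +3.8 |
| 0.9 | -0.68 | -0.48 | +4.3 |

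Measured from day 0 to day 14, the same series give 0, +5.0 and +5.0.

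**In scale points.** A second simulation rounded scores and clipped them to 0-64, assuming mean 8, between-patient SD 4, within-patient SD 1 to 4 and correlation 0 to 0.8:

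- Flat series: -0.9 to -5.5 points.
- Rise to +10 points by day 3, sustained (within-patient SD 2): reported as -1.3 to -2.3, against +9.9 from day 0.
- Transient 10-point peak at days 3-4 (SD 2): reported as -10.5 to -11.3; day 0 to last day is about 0.
- Rise starting only after day 7 and reaching +10 (SD 2): reported as +7.1 to +8.2, against +9.9 from day 0.

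**Share of patients falling with no true change.** 74% to 89% on the unbounded normal series (correlation 0.9 to 0), and 62% to 87% after rounding and clipping. With assumed low scores (mean 1, between-patient SD 2, within-patient SD 1) it is 43% to 65%. This figure depends heavily on the assumptions.

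**Missing items.** Summing the answered items scores each blank as 0. If 4 of 16 items are skipped (assumed) and symptoms are even across items, a true total of 20 becomes 20 x 12/16 = 15. Sections 8.1.4 and 8.1.5 set missing-item rules for HADS and ItchyQoL; Section 9.2.1 sets none for SOWS.

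**The case against.** The best defence is that this is an extra summary. Section 9.2.1 ties the objective on daily changes to the 14-day daily displays, and a week-1 peak would appear in the daily items, the daily totals, the peak categories and the daily maximum symptom score. Section 9.1.7 also analyses adverse events suggesting abuse potential or withdrawal, including in the washout period. This stands. A reader might infer that the plan hides withdrawal or cannot show a rise at all; the document does not support that, because those displays remain and a rise starting after day 7 still appears in the change score, only reduced. What the defence leaves open is that the other displays show levels by day or by peak category. None gives a within-patient change.

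The statistic could also be read as how far symptoms resolve from their early peak. That is a legitimate quantity, but it is not what the label says.

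A caution applies to the remedy as well. Change from day 0 to the maximum of days 1-14 has the mirror fault: on the same flat series it shows a false rise of about +0.95 to +1.7 SD. Nor can day 0 simply be called the last on-drug score. Section 3.1 places the visit after the last week of drug, and under Sections 3.2.1 and 3.2.2 patients who stop early attend it after discontinuing.

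Finally, the magnitudes rest on assumed SDs and correlations, and the SAP does not say how often items are skipped.

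**Conclusion.** The point holds for this one summary. As defined, the change is biased towards improvement, and that direction follows from the definition. Its size is assumption-dependent: about 0.7 to 1.4 within-patient SD on a flat normal series for correlation 0.9 to 0. The statistic can report a sustained rise reached by day 7 as a fall, it understates a later rise, and it cannot be positive when the last diary entry is by day 7. No single percentage of patients falsely improving should be quoted.

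This should be fixed but is not critical. The summary is descriptive and secondary, the primary endpoint is treatment-emergent adverse events, no inference is planned, and the unbiased daily totals are already in the plan. The missing-item rule is a lesser point in the same section.

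**What to change.** In Section 9.2.1:

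1. Take the SOWS total on the End of Treatment visit date as the reference. State that this score may already be off drug, particularly for patients who stopped early.
2. Summarise change from that reference to each later washout day and to the Washout and Safety Follow-up visit, in line with Section 8.2.
3. Keep the present statistic only under a name such as peak (days 0-7) to end of washout.
4. If change to the 14-day peak is reported, state beside it that it is biased upwards.
5. Prorate the total (mean of answered items x 16) when few items are missing, with the limit stated; otherwise set it to missing.

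The cost is SAP wording and programming. Scores are collected daily from the End of Treatment visit, so no new data are needed.
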